5. ENDPOINTS

5.1 PRIMARY ENDPOINTS

The primary objective (to find the MTD) is determined from the primary endpoint, DLT.

Maximum tolerated dose (MTD):

MTD is defined as the highest dose studied for which the incidence of DLT in an individual dose cohort is at most 33% during the first course.

Additionally, all information, including DLT from later treatment courses, will be considered in the final determination of the dose recommended for Phase II.

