#### 4.1.3 Selection of doses in trial

##### 4.1.3.1. First course of administration of BI 6727

The starting dose will be 12 mg. As long as no patient of an ongoing dose tier develops drug-related toxicity beyond Grade 1 according Common Terminology Criteria for adverse events (CTCAE) during the initial treatment course the dose will be escalated by up to 100% in new patients. As soon as any patient of an ongoing dose tier experienced drug-related toxicity Grade 2 or higher escalation steps of not more than 50% will be allowed thereafter. Should dose limiting toxicity (DLT) be observed in 1/6 patients treated in a cohort and escalation continues this will be in steps of not more than 35%. Before entering patients at a higher dose level it will be ensured that all patients at an ongoing dose level have completed the initial course of BI 6727 dosing. The decision regarding the incremental size of the dose escalation steps will only be taken after discussion between the sponsor and the clinical investigator considering toxicity data from each patient cohort. Prior to inclusion of a new patient the investigator has to confirm the respective dose with the clinical monitor of the sponsor.

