#### **4.1.6 Selection and timing of doses for each subject**

BI 6727 will be administered as a short infusion over 60 minutes using an infusion pump, on day 1 of each course (the start and end time of the infusion needs to be documented in the e-CRF). Immediately following the infusion of BI 6727 the infusion tubing will be washed with 100 mL physiological sodium chloride (0.9% NaCl) solution for a maximum duration of 10 minutes (The end time of the washing step needs to be documented in the e-CRF). BI 6727 should be administered strictly intravenously.

Initially, three patients will be treated per dose level. When at the ongoing dose level one patient experiences drug-related dose limiting toxicity (DLT; for definition, please refer to section 5.2.1) the number of patients treated at that dose level will be increased to a maximum of six evaluable patients. When no further patient experiences DLT the dose will be escalated to the next level. When two or more patients experience DLT in any dose cohort, other than the

expansion cohort at MTD level, enrolment into this dose cohort will be stopped. In order to define the maximum tolerated dose (MTD) three additional patients will be treated at one dose tier below unless six have already been treated at that dose tier. The MTD (see also section 5.2.1) is the highest dose at which not more than one patient out of six experiences DLT (R01-0028). Should safety data of patients treated at the next lower dose indicate a sufficient safety margin another escalation to an intermediate dose can be chosen after discussion between the investigator and the clinical monitor.

Once the MTD is determined patient enrolment at higher dose tiers will be suspended. Further patients will be included at the MTD level until a total of 24 patients will have been treated at the MTD.

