## 5.2 SAFETY

### 5.2.1. Maximum tolerated dose (MTD) and dose limiting toxicity (DLT)

The maximum tolerated dose is defined as:

The dose of BI 6727 which is one dose tier below that dose at which two or more out of a maximum of six patients experienced DLT. At the maximum tolerated dose, no more than one patient out of six patients may experience DLT, i.e. MTD is defined as the highest dose studied for which the incidence of dose-limiting toxicity is no more than 17% (i.e. 1/6 patients) during the first course.

For definition of DLT, it is essential that patients are treated sufficiently according to supportive care standards. Patients with treatable adverse events that are not sufficiently treated need to be replaced.

Dose limiting toxicity is defined as:

- drug related CTCAE grade 3 or 4 non haematological toxicity (except emesis or diarrhoea responding to supportive treatment), or
- drug related CTCAE grade 4 neutropenia for seven or more days and / or complicated by infection, or
- CTCAE Grade 4 thrombocytopenia .

The MTD will be defined on the basis of DLT observed during the first course of dose escalation cohorts. However, for those patients who receive a further infusion, unusual or unexpected toxicities will be considered for the purposes of confirming the MTD.

Patients with a clinical benefit after a course of BI 6727 (symptom improvement, clinical response or absence of progression) and who recovered from drug related adverse events are eligible for a further treatment course. In case of symptom improvement despite disease progression a repeated course may be allowed in agreement between the clinical monitor and the investigator. All DLT's occurring during the first or repeated treatment courses will be reported as significant adverse events.

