### 7.3.1 Primary analyses

Non evaluable patients will be replaced. The total number of study patients depends on the toxicity encountered. Patients who are evaluable for toxicity but not for efficacy need not be replaced.

The primary endpoint for this study is the tolerability and safety of BI 6727 as reflected by the Maximum Tolerated Dose (MTD) of BI 6727

Determination of MTD will be done using data from patients receiving the first course of BI 6727. Depending on the drug related toxicity observed in this study, up to six patients will be treated in each dose cohort. To increase the safety database at the presumed Phase II dose, a total of 24 patients will be enrolled at MTD.

MTD will be defined as the dose of BI 6727 that is one dose cohort below that dose at which two or more out of a maximum of six patients experienced DLT. At the maximum tolerated dose, no more than one patient out of six patients may experience Dose Limiting Toxicity (DLT, for definition, see section 5.2.1).

MTD will be defined on the basis of DLT observed during the first course. However, for those patients who receive a further infusion, unusual or unexpected toxicities will be considered for the purposes of confirming the MTD

To assess safety of BI 6727, all DLT's occurring during the first or repeated treatment courses will be reported as significant adverse events.

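### SAP 5.1 puts the MTD limit at 33% DLT where the protocol allows at most 1 in 6 (17%), so a dose with 2/6 DLTs may be classified differently by the two documents

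*SAP*

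**What the plan says.** **Protocol.** Three sections give the same limit.
- Section 4.1.6: the MTD "is the highest dose at which not more than one patient out of six experiences DLT". Three patients are treated first, and one DLT expands the cohort to at most six evaluable patients. At two or more DLTs, "enrolment into this dose cohort will be stopped" (the expansion cohort at the MTD is exempt).
- Section 5.2.1: "MTD is defined as the highest dose studied for which the incidence of dose-limiting toxicity is no more than 17% (i.e. 1/6 patients") in course 1. It adds: "The MTD will be defined on the basis of DLT observed during the first course of dose escalation cohorts".
- Section 7.3.1: the MTD is "one dose cohort below that dose at which two or more out of a maximum of six patients experienced DLT".

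**SAP.** Section 5.1 takes the highest dose at which "the incidence of DLT in an individual dose cohort is at most 33% during the first course". It treats the dose recommended for phase II as a separate decision that also uses later courses. Section 4, which lists changes to the planned analysis, covers tumour-response endpoints and the ECG analysis that followed Amendment 3. It does not mention the MTD limit. Section 3 says the SAP covers the protocol of 3 October 2005 and three amendments up to 26 June 2008. Only the October 2005 protocol was supplied.

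**The concern.** The stated limit on the primary endpoint doubles between the two documents, and no readable text explains why. SAP 3.2 still describes a 3+3 design and cites the same reference that protocol 4.1.6 cites for its one-in-six rule.

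The cohort result that separates the rules is 2/6. By the protocol that dose is above the MTD, and the MTD is the next lower tier if that tier qualifies. By the SAP, with 33% read as one third, the 2/6 dose can itself be the MTD. SAP 7.7 says its tables document the data behind the MTD selection, so the report has to rest on one definition. What is at stake is the dose that the report names as the MTD.

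**Working it through.** **1. The protocol's own figure.** Table 7.6: 1 gives the probability of two or more DLTs in six patients. With q = 1 − p this is 1 − q⁶ − 6pq⁵:
- p = 0.40: 0.7667 (stated 0.77)
- p = 0.42: 0.7965 (stated 0.80)
- p = 0.45: 0.8364 (stated 0.84)

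The table reproduces, and it rests on the 1/6 rule. If 2/6 is acceptable, a six-patient cohort fails only with three or more DLTs. The probabilities become 0.456, 0.497 and 0.558, and the true rate needed for an 80% chance of failing rises from 0.42 to about 0.585.

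**2. Counts that each limit admits.**

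| Limit | n = 3 | n = 6 |
|---|---|---|
| 17% | 0 | 0, 1 |
| 33% taken literally | 0 | 0, 1 |
| one third | 0, 1 | 0, 1, 2 |

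Since 2/6 = 33.33%, it fails a literal 33% and meets one third. A 1/3 cohort is expanded to six under protocol 4.1.6, so 2/6 is the result that matters. Results of 2/4 (50%) and 2/5 (40%) fail every limit.

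**3. Probability of ending at 2/6 on first ascent.** The first three patients must have exactly one DLT, probability 3pq². The rest depends on how patients 4 to 6 enter, because enrolment stops at the second DLT:
- One at a time: patients 4 and 5 have no DLT and patient 6 has one, pq². Product: 3p²q⁴.
- Patient 4 alone, then 5 and 6 together: 6p²q⁴.
- All three already enrolled: exactly one DLT among them, 3pq². Product: 9p²q⁴.

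| True DLT rate p | 3p²q⁴ | 6p²q⁴ | 9p²q⁴ |
|---|---|---|---|
| 0.20 | 0.0492 | 0.0983 | 0.1475 |
| 0.33 | 0.0658 | 0.1317 | 0.1975 |
| 0.42 | 0.0599 | 0.1198 | 0.1797 |

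Example: at p = 0.33, p²q⁴ = 0.1089 × 0.2015 = 0.02194, and three times this is 0.0658. All three expressions peak at p = 1/3. A simulation of 10⁶ runs with the stopping rule gave 0.0664, 0.1313 and 0.1977 at 0.33, and 0.0602, 0.1194 and 0.1790 at 0.42.

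**4. Probability that a dose qualifies on first ascent.** By the protocol, 0/3 passes, or 1/3 followed by 0/3: q³ + 3pq⁵. By the SAP read as one third, add the step 3 values (lowest to highest).

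| p | Protocol | SAP as one third |
|---|---|---|
| 0.20 | 0.7086 | 0.7578 to 0.8561 |
| 0.33 | 0.4344 | 0.5003 to 0.6319 |
| 0.42 | 0.2778 | 0.3377 to 0.4575 |

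The last column is the chance that a dose would meet the SAP definition; escalation itself follows the protocol. The 0.2778 exceeds the 0.20 implied by Table 7.6: 1 because a 0/3 cohort passes without being expanded to six.

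**5. Size of one tier.** Under protocol 4.1.3.1, "the dose will be escalated by up to 100% in new patients" while toxicity stays at grade 1 or below. The cap is 50% after grade 2 or higher toxicity and 35% after 1/6 DLTs. Section 4.1.6 can narrow the gap, since "another escalation to an intermediate dose can be chosen after discussion between the investigator and the clinical monitor".

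**The case against.** **Literal reading.** As written, 33% is below one third, so 2/6 fails and the documents agree for the planned cohort sizes. The protocol's 17% is rounded up and annotated as 1/6; the SAP's 33% is rounded down and carries no count. This stands as arithmetic, and it makes the effect conditional. However, a literal 33% admits exactly the counts that 17% admits in cohorts of three or six, so the new number would do nothing there. Rounding to a whole percent, as the protocol does for 1/6, turns one third into 33%. The text does not settle which reading was meant.

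**Unseen text.** An amendment may have changed the limit, in which case the SAP is following the amended protocol. The SAP describes other features absent from the supplied protocol, such as the 2-hour infusion. Part of SAP 7.7.1.1, on MTD and DLT, is redacted. Both points stand and limit confidence. The remedy covers either case.

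**Small consequence.** The protocol governs escalation, SAP 7.7 is descriptive, and SAP 3.2 already names 300 mg as the recommended phase II dose. First-course DLT counts are tabulated by initial treatment, so a reader can apply either limit. Nothing shows that any cohort had 2/6. All of this stands; it confines the problem to the dose named as the MTD, which is still the primary endpoint.

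**The probabilities.** They are prospective, use assumed DLT rates and enrolment patterns, and leave out a tier that passes with 0/3 and is later expanded on de-escalation. They give the chance of reaching the disputed result at one dose, which is not the chance that the reported MTD changes.

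**Conclusion.** The concern holds. The SAP's primary-endpoint limit is wrong as written against the only protocol text supplied, and the change is not declared. Confidence is moderate because the amendments were not available.

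The numerical effect requires 33% to mean one third. On that reading, a dose reaches the disputed 2/6 result on first ascent with probability 0.05 to 0.15 at a true DLT rate of 0.20, 0.07 to 0.20 at 0.33 and 0.06 to 0.18 at 0.42. The named MTD could then be one tier higher than the protocol allows. If 33% is literal, the difference is zero for cohorts of three or six. Neither reading affects how patients were dosed.

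**What to change.** Restate SAP 5.1 so that the MTD is the highest dose with at most one DLT among six evaluable patients, counted in the first course and in the dose escalation cohorts only.

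If one of the three amendments changed the limit, cite it in SAP Section 4, and give the limit in SAP 5.1 as a count out of six, saying explicitly whether 2/6 qualifies. Reporting the MTD under both definitions is then not needed.

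The cost is SAP wording only: one sentence in 5.1, and one in Section 4 if an amendment is the source.

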5.2 SECONDARY ENDPOINTS

5.2.1 Tumour response

For solid tumours, evaluation of tumour response will be assessed according to the Response Evaluation Criteria in Solid Tumours (RECIST) definition. The overall response of target and non-target lesions together with or without the appearance of new lesions as reported by the investigator is assessed on a four point categorical scale as complete response (CR), partial response (PR), stable disease (SD), and progressive disease (PD) according to the RECIST criteria ([R01-0754](#)). However, for the analyses within this TSAP, a modified version of the RECIST criteria will be used, in order to best handle measurements that are non-evaluable (NEV). [REDACTED] Basically, an algorithm is used to determine the outcome, depending on whether the NEV measurement is for target / non-target lesions. If it is still not possible to determine the outcome based upon the algorithm, then a clinical assessment will be used.

Tumour responses will be analysed based on the ‘Overall response’ question that is asked directly from the Electronic Case Report Form (eCRF). Additionally, clinical progression will be taken into account. It will not be checked whether the answer of the overall response assessment was based on RECIST only or already incorporates clinical progression, i.e. no differentiation will be made between NEVCPD or PD.

Using the RECIST criteria combined with the presence or absence of clinical progression, several endpoints will be analysed and created. Whilst some are at each tumour assessment (unconfirmed), others are summary measures over time (confirmed / best).

Note that for the case of non-target responses, level=2 refers to ‘Incomplete response / Stable disease / Partial response’.

The main endpoints with their corresponding definitions are as defined below:

Unconfirmed Overall Response: [REDACTED]

[REDACTED] As noted above, for some patients the overall response as reported by the investigator also includes information about clinical progression and is

assigned to progressive disease as soon as a patient experiences clinical progression. For that reason this endpoint is referred to Unconfirmed Overall Response and not to Unconfirmed RECIST Overall Response. Analogous to RECIST, the endpoint Unconfirmed Overall Response will be made up of 6 potential outcomes with 5 ordered levels:

Unconfirmed Overall Response	Abbreviation	Level
Complete response	CR	1
Partial response	PR	2
Stable disease	SD	3
Non-evaluable but clinically non progressive disease	NEVCNPD	4
Progressive disease or Non-evaluable but clinically progressive disease	PD or NEVCPD	5

Unconfirmed Best Overall Response: This is the best of the individual 'Unconfirmed Overall Responses', recorded from the start of the treatment until PD.

Unconfirmed Best Objective Response: If the 'Unconfirmed Best Overall Response' is either CR or PR, then this Unconfirmed Best Objective Response is Yes. Otherwise it is No.

Additional supportive endpoints are:

Clinical Benefit: Clinical benefit is defined as the absence of disease progression (no PD or NEVCPD) during a course.

Confirmed objective response: To confirm an objective status here, changes in tumour measurements must be confirmed by at least one later assessment that must be performed \geq 28 days after the criteria for CR or PR are first met without having an assessment of PD or NEVCPD.

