## FLOW CHART: INITIAL TREATMENT COURSE

Study Periods	Screening	Treatment	Observation after Treatment						EOT f	FU
			course 1							
Visit	1	2	3	4	5	6	7	8		
Day	-14 - 0	1	2	3	5	8	15	22		
(day range)				(±1)	(±1)	(±1)	(±1)	(±2)		
Informed Consent and Subject Information	x									
Demographics	x									
Genotyping		x j								
Medical History	x									
In- /Exclusion Criteria	x	x								
Physical Examination	x								x	x b
ECOG performance score	x	x						x	x	x
Pregnancy test	x									
MRI, CT a	x							x a		x
EUS, US (optional)	x							x		x
Body weight	x	x							x	
ECG	x	x k						x		x b
Infusion BI 6727	x									
Vital Signs	x	x	x	x	x	x	x	x		
Safety lab parameters	x	x	x	x	x	x	x	x		x b
Tumour markers i	x							x		
Urine examination	x		x						x	
Pharmacokinetics (plasma)		x c	x c	x c	x c	x c	x c			
Pharmacokinetics (urine)		x h	x h	x h						
Adverse Events	x	x	x	x	x	x	x	x	x	x e
Concomitant Therapy	x	x	x	x	x	x	x	x		
Tumour assessment a	x							x a		x
Conclusion of Subject Participation									x	

a according to RECIST guidelines. Imaging and assessment are required at the end of every other treatment course.b optionalc for time schedule of pharmacokinetic sampling refer to table (Appendix 10.2), plasma samples have to be drawn from the opposite arm of the infusion. For patients having central venous access, BI 6727 may be administered using this device and PK samples obtained from either forearm. Intensive PK blood sampling performed in Course 1 only; for repeated courses PK blood sampling performed at the end of infusion (1:00h) after 24:00h, 168:00 h and after 336:00h (Appendix 101.2).e if not yet recovered at the end of the previous course and in case of new adverse events if drug relatedf end of treatment; investigations which have to be performed at the last visit (when a patient discontinues the study)g data from visit 8 may be used in case EOT examinations were done within the past four weeks

FU= follow up visits until progression, lost to follow up or treatment with another anti-cancer drug

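### SAP best overall response can tabulate a patient with measurable disease as NEVCNPD although a later scan shows progression, a case that Protocol 10.4.5 can treat as progressive

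*SAP*

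**What the plan says.** SAP 5.2.1 states that "the endpoint Unconfirmed Overall Response will be made up of 6 potential outcomes with 5 ordered levels". The levels are CR 1, PR 2, SD 3, then "Non-evaluable but clinically non progressive disease" (NEVCNPD) at 4, and "Progressive disease or Non-evaluable but clinically progressive disease" (PD or NEVCPD) at 5. Unconfirmed Best Overall Response is then defined as the best of these individual ratings, "recorded from the start of the treatment until PD". Ratings come from the overall response question on the eCRF, with clinical progression taken into account. For non-evaluable measurements the SAP describes an algorithm that depends on whether target or non-target lesions are affected, and adds: "If it is still not possible to determine the outcome based upon the algorithm, then a clinical assessment will be used". Part of this text is redacted. SAP 7.5 tabulates best overall response by initial treatment.

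Protocol 10.4.5 covers target lesions that become non-evaluable. If imaging is missing at one time point and lesions are measured during the next course, the earlier rating is revised in the light of the later one. A later PD turns it into a non-evaluable, progressive category (NEVPD). A later response or stable disease turns it into a non-evaluable, non-progressive one (NEVNPD).

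Two other provisions matter. Footnote a of the Protocol flow charts says: "Imaging and assessment are required at the end of every other treatment course". Protocol 7.3.2 assigns an overall response of NEV to any patient without a measurable lesion, and Protocol 3.3.1 requires measurable disease only of the 18 additional patients at the MTD.

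**The concern.** NEVCNPD records that the tumour could not be assessed; it is not a finding about the tumour. Ranking it above PD lets one such rating override a later scan that shows progression. The protocol has a rule that treats at least part of these cases as progressive. The SAP's six outcomes and its abbreviation list contain neither NEVPD nor NEVNPD, and SAP Section 4, which lists changes to the planned analysis, does not say that the rule was dropped.

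At stake is the PD row of the best overall response table, which reports a secondary endpoint by dose. A patient moved out of that row appears as non-evaluable instead. Whether this happens depends on how sites record ratings when no usable scan exists, not on the drug. Dose cohorts hold three to six patients, so a single move is visible.

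**Working it through.** The plan states no PD proportion and no frequency of non-evaluable ratings, so there is no figure to reproduce. The check applies the stated rule to sequences of ratings.

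**Inputs.** Levels from SAP 5.2.1: CR 1, PR 2, SD 3, NEVCNPD 4, PD/NEVCPD 5. Reassessment rule from Protocol 10.4.5. Cohort sizes from the Protocol synopsis: 3 to 6 per level, 24 at the MTD.

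**Rule.** Best response = the minimum level over all ratings up to and including the first level-5 rating. The level-5 rating is included because a patient whose first rating is PD would otherwise have no best response. For NEVCNPD followed by PD, both readings give NEVCNPD.

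**With Protocol 10.4.5.** A NEVCNPD rating directly followed by PD is first changed to NEVPD. The SAP gives NEVPD no level; level 5 is assumed here.

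| Sequence | SAP as visibly written | 10.4.5 applied first |
|---|---|---|
| PD | 5: PD | 5: PD |
| NEVCPD, PD | 5: PD/NEVCPD | 5: PD/NEVCPD |
| PD, NEVCNPD | 5: PD (counting stops) | 5: PD |
| NEVCNPD, PD | min(4, 5) = 4: NEVCNPD | min(5, 5) = 5: progressive |
| NEVCNPD, NEVCNPD, PD | min(4, 4, 5) = 4: NEVCNPD | 4: NEVCNPD, if the rule reaches back one time point |
| SD, PD | 3: SD | 3: SD |
| NEVCNPD, SD, PD | 3: SD | 3: SD |

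Only patients with NEVCNPD before PD and no CR, PR or SD are affected. The protocol rule resolves a single NEVCNPD but not a run of two. Read literally, it also needs measurements in the next course, whereas imaging is scheduled every other course. Reassessment alone may therefore not reach every case.

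**Size in one cohort.** One reclassified patient changes a row by 1/6 = 16.7 points with six patients and by 1/3 = 33.3 points with three.

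**Size at the MTD (assumed inputs, not from the documents).** Let p be the share of 24 patients with PD and no earlier CR, PR or SD, and q the share of those rated NEVCNPD first. The PD share shown is p(1 − q), and the number of patients moved is 24pq.

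| p | q = 0 | q = 5% | q = 10% | q = 20% |
|---|---|---|---|---|
| 40% | 40% (0 moved) | 38% (0.48) | 36% (0.96) | 32% (1.92) |
| 60% | 60% (0 moved) | 57% (0.72) | 54% (1.44) | 48% (2.88) |

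Over q from 5% to 20%, about 0.5 to 2.9 patients of 24 move. At q = 0 nothing changes.

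**The case against.** The SAP says that it adds detail to the protocol's analyses and nowhere withdraws 10.4.5, so the rule may be meant to apply. The redacted text could contain it. This stands as a reason not to claim that the PD row will be wrong. It does not settle the matter: the ordered scale and the best-of rule are fully visible, and the algorithm is described only in terms of target and non-target lesions, which is a choice within one time point rather than a revision after a later scan.

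The frequency is also open. A reader might infer that NEVCNPD ratings before the first scan are routine, because imaging is due only every other course and retreatment under Protocol 3.3.3 calls for a judgement of benefit. The documents do not show that this judgement is entered as an overall response. The SAP ties unconfirmed responses to tumour assessments, and the eCRF is not among the documents. On the other side, SAP 5.2.2 provides for a NEVCNPD assessment dated after the last imaging, so such ratings without a scan are at least foreseen.

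A further objection concerns the remedy. Dropping NEVCNPD from best response for everyone would introduce a new error. Patients without measurable lesions are NEV by rule, so NEVCNPD is how their non-progression is recorded. One who stayed clinically stable for many courses and then progressed would be shown as best response PD. This objection stands in full and limits the fix.

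**Conclusion.** The point holds for patients with measurable disease: on the visible text, NEVCNPD followed by PD, with no CR, PR or SD, is tabulated as NEVCNPD, and the PD row can be understated. Where a single missed imaging time point is followed by PD in the next course, this differs from Protocol 10.4.5.

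Two stronger readings are not supported. One is that any patient whose only evaluable scan shows PD drops out of the PD row; without an earlier NEVCNPD rating, that patient is still tabulated as PD. The other is that progression is known to be understated, or by a large amount; the frequency is not documented and the relevant text is partly redacted.

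The effect is confined to one row of a descriptive table and its NEVCNPD counterpart. Objective response depends only on CR and PR, progression-free survival takes progression at its own date, and the by-timepoint table still shows each PD. No PD-rate endpoint is defined. The size is 17 to 33 percentage points per reclassified patient in a cohort of six to three, and about 0.5 to 2.9 of 24 patients at the MTD under the assumed p and q.

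**What to change.** Add to SAP 5.2.1:

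- The reassessment in Protocol 10.4.5 is applied before best overall response is derived, with NEVPD placed at level 5.
- In patients with measurable disease, NEVCNPD is the best overall response only when there is no CR, PR, SD or PD/NEVCPD assessment. This also settles repeated NEVCNPD ratings before PD.
- In patients with no measurable lesion, NEVCNPD remains a separately reported category.
- The by-timepoint table keeps NEVCNPD as recorded.

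The change should be limited to the best-response derivation, so that progression dates under SAP 5.2.2 do not move. If the redacted algorithm already does this, one visible sentence saying so is enough. The cost is one extra derivation step and a split by measurable disease at baseline. The reported PD proportion may become slightly less favourable.
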